10.3 Clinical laboratory evaluations

Laboratory values, including markedly abnormal laboratory values will be presented descriptively by treatment group for SS up to Week 56. Markedly abnormal values and shifts from baseline (Week 0) will be presented for the SS through Week 24 and BKZ set through initial and maintenance treatment period.

The markedly abnormal tables and those based on CTCAE grade will be produced only for selected laboratory variables.

For tables where data are summarized by visit, unscheduled and repeat visits will not be summarized, but these data will be included in listings. For tables where multiple measurements over a period of time are considered (as in shift tables), unscheduled and repeat visits will be considered as long as they were collected in the period being summarized. All summaries will be presented in SI units and will be based on observed case values. In the case where laboratory values are below the lower limit of quantification, then these will be set to the midpoint between 0 and the lower limit of quantification for the purpose of summarizing the data. The following summaries are required:

- A summary of the absolute and change from Baseline values in each laboratory variable by treatment group and visit
- A summary of the number and percentage of subjects experiencing markedly abnormal values at any time while on treatment (assessment on or following the first dose of study treatment through the final dose of study treatment + 140 days) by laboratory variable and treatment group
- A summary of the number and percentage of subjects with a given CTCAE grade (0, 1, 2, 3, or 4) based on minimum/maximum post-baseline value by laboratory variable and treatment group
- A shift table of the number and percentage of subjects experiencing CTCAE grade 0, 1, 2, 3 or 4 values (as applicable) at Baseline to minimum/maximum post-Baseline CTCAE grade, by laboratory variable and treatment group

For laboratory summaries through week 24, the cut off will be the earliest of week 24 or last dose + 140 days.

For laboratory shift tables through week 24, the treatment groups BKZ 320mg Q4W, BKZ 320mg Q4W/Q8W, BKZ Total and ADA will be presented.

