For laboratory shift tables through initial and maintenance treatment period, the treatment groups BKZ 320mg Q4W, BKZ 320mg Q4W/Q8W, ADA/ BKZ 320 mg Q4W and BKZ Total will be presented. For subjects randomized to ADA, only data after the switch to Bimekizumab will be considered. The last value prior to the switch will be considered as baseline.

A by-subject listing of all laboratory data will be provided. This listing will be presented by treatment group and will include: center, subject identifier, age, sex, race, weight, visit, laboratory variable, result (with abnormal values flagged as “L” or “H” accordingly) and unit.

Markedly abnormal values are defined as those with a severity of Grade 3 and above based on the common terminology criteria for adverse events (CTCAE) criteria (U.S. Department of Health and Human Services 2010). Definitions of markedly abnormal values using the Grade 3 cut points are given in the tables below for age ranges of ≥ 17 years (Table 10–1 for markedly abnormal biochemistry values and Table 10–2 for markedly abnormal hematology values).

Tables summarizing markedly abnormal values should include a summary (counts and percentages) of markedly abnormal labs observed at any time while on treatment (ie, treatment-emergent markedly abnormal [TEMA]). For this summary, Baseline values and values observed more than 140 days after the last administration of study medication are not considered. The laboratory results classified as Grade 3 or Grade 4 will be summarized and listed separately.

Summaries in the ADA/BKZ arm will be provided to examine markedly abnormal labs occurring within 70 days and >70 days of the treatment switch. The time since the treatment switch is calculated as the number of days since the final dose of adalimumab. Only lab values recorded after the start of bimekizumab treatment will be included. 70 days was chosen as it is approximately equal to five half lives of adalimumab.

Table 10–1: Definitions of Markedly Abnormal Biochemistry Values

Parameter name	Conventional		Standard		Abnormal Designation
	Unit	Criteria	Unit	Criteria	
Creatinine	mg/dL	>3.0 x ULN	mmol/L	>3.0 x ULN	AH
Glucose	mg/dL	<40 >250	mmol/L	<1.7 >13.9	AL AH
Calcium	mg/dL	>12.5 <7.0	mmol/L	>3.1 <1.75	AH AL
Magnesium	mg/dL	>3.0 <0.9	mmol/L	>1.23 <0.4	AH AL
Potassium	mmol/L	>6.0 <3.0	mmol/L	>6.0 <3.0	AH AL
Sodium	mmol/L	>155 <130	mmol/L	>155 <130	AH AL

Table 10–2: Definitions of Markedly Abnormal Hematology Values

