10.4 Vital signs, physical findings, and other observations related to safety

10.4.1 Vital signs

The following vital signs variables should be summarized: systolic blood pressure (mmHg), diastolic blood pressure (mmHg), body temperature (°C) and heart rate (beats/min). The following summary will be provided:

- A summary of the absolute and change from Baseline value for each vital sign variable by treatment group and visit through initial and maintenance treatment period for the SS
- A summary of the number and percentage of subjects experiencing at least one markedly abnormal value for a vital sign variable as defined in Table 10–3, by treatment group, through Week 24 for the SS and through initial and maintenance treatment period for the BKZ set

Table 10–3: Definitions of Markedly Abnormal Blood Pressure Values

Parameter (unit)	Markedly Abnormal Low	Markedly Abnormal High
Systolic blood pressure (mmHg)	<90 and a decrease from Baseline of \geq 20	>180 and an increase from Baseline of \geq 20
Diastolic blood pressure (mmHg)	<50 and a decrease from Baseline of \geq 15	>105 and an increase from Baseline of \geq 15

A by-subject listing of all vital signs data should be provided. This listing should be presented by treatment group and will include: center, subject identifier, age, sex, race, weight, visit, vital sign variable and result (with abnormal values flagged as “L” or “H” accordingly).

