12.2 Appendix A: Definition of CTCAE grades

Table 12–1: Definitions of CTCAE grades by biochemistry parameter

Parameter (unit)	Definition	Unit	Grade 1	Grade 2	Grade 3	Grade 4
Creatinine	High	mmol/L	>ULN-1.5 x ULN	(>1.5 – 3.0) x ULN	(>3.0 – 6.0) x ULN	6.0 x ULN
Sodium	Low	mmol/L	130-<LLN	N/A	120-<130	<120
Sodium	High	mmol/L	>ULN-150	>150-155	>155-160	≥160
Potassium	Low	mmol/L	3.0-<LLN	3.0-<LLN	2.5-<3.0	<2.5
Potassium	High	mmol/L	>ULN-5.5	>5.5-6.0	>6.0-7.0	>7.0
Calcium	Low	mmol/L	2.0-<LLN	1.75-<2.0	1.5-<1.75	<1.5
Calcium	High	mmol/L	>ULN-2.9	>2.9-3.1	>3.1-3.4	>3.4
Magnesium	Low	mmol/L	0.5-<LLN	0.4-<0.5	0.3-<0.4	<0.3
Magnesium	High	mmol/L	>ULN-1.23	N/A	>1.23-3.30	>3.30

Subjects who meet the decreased potassium criteria of 3.0-<LLN, which is specified as the criteria for both CTCAE grade 1 and grade 2, will be counted as CTCAE grade 2.

Table 12–2: Definitions of CTCAE grades by hematology parameter

Parameter (unit)	Definition	Unit	Grade 1	Grade 2	Grade 3	Grade 4
Hemoglobin	Low	g/L	100-<LLN	80-<100	<80	N/A
Hemoglobin	High	g/L	>0-20 above ULN	>20-40 above ULN	>40 above ULN	N/A
Platelets	Low	10 ⁹ /L	75-<LLN	50-<75	25-<50	<25
WBC	Low	10 ⁹ /L	3-<LLN	2-<3	1-<2	<1
WBC	High	10 ⁹ /L	N/A	N/A	>100	N/A
Lymphocytes	Low	10 ⁹ /L	0.8-<LLN	0.5-<0.8	0.2-<0.5	<0.2
Lymphocytes	High	10 ⁹ /L	N/A	>4-20	>20	N/A
Neutrophils	Low	10 ⁹ /L	1.5-<LLN	1.0-<1.5	0.5-<1.0	<0.5

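### Laboratory values already markedly abnormal before first dose, or before the switch to bimekizumab, are counted as treatment-emergent if they persist

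*SAP*

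**What the plan says.** SAP 10.3 sets the threshold by absolute cut points: "Markedly abnormal values are defined as those with a severity of Grade 3 and above". The cut points are in Tables 10-1 and 10-2, with a separate list of multiples of the upper limit of normal for ALT, AST and bilirubin. The summary then covers "markedly abnormal labs observed at any time while on treatment (ie, treatment-emergent markedly abnormal [TEMA", over the window "assessment on or following the first dose of study treatment through the final dose of study treatment + 140 days". Baseline is mentioned once in the counting rule: "For this summary, Baseline values and values observed more than 140 days after the last administration of study medication are not considered".

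For the adalimumab-to-bimekizumab arm there is a further summary, split at 70 days from the last adalimumab dose. Its one added restriction is: "Only lab values recorded after the start of bimekizumab treatment will be included".

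The same section plans shift tables from Baseline CTCAE grade to worst post-Baseline grade. For subjects randomised to adalimumab, the shift table through the maintenance period has its own reference: "The last value prior to the switch will be considered as baseline". SAP 3.2 confines that bimekizumab Baseline, for laboratory data, to the shift tables.

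**The concern.** The label treatment-emergent tells a reader that the abnormality arose after treatment began. The rule requires only that it was seen after treatment began. A subject with a high glucose before and after first dose meets it. So does a subject with raised transaminases on adalimumab at Week 24 that persist on bimekizumab.

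Two outputs are most exposed:

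- **The post-switch summary.** It has no concurrent control, so a carried-over value has nothing to be set against and reads as a finding on bimekizumab.
- **The BKZ Set summary.** SAP 3.6 pools adalimumab-arm data after Week 24 into the Q4W column for safety, so an abnormality that began on adalimumab can also appear in a main bimekizumab table.

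Markedly abnormal counts are likely to be small, so a few carried-over subjects could change how such a table reads.

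**Working it through.** The plan gives no expected count and no Baseline prevalence, so there is no figure to reproduce. The check is of the text, followed by an illustration on assumed rates.

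**1. How the SAP treats the same idea elsewhere**

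- Adverse events (10.2.1): the start date must fall on or after first dose. Onset is required.
- Blood pressure (10.4.1, Table 10-3): a low value must be below the cut point "and a decrease from Baseline of" a stated amount, and the high limits are built the same way. A change is required.
- Laboratory values (10.3): neither onset nor change is required.

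**2. Who can be markedly abnormal beforehand**

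Protocol exclusion 19, against the Grade 3 low cut points in SAP Table 10-2:

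| Parameter | Excluded at Screening if below | Grade 3 if below |
|---|---|---|
| Hemoglobin, g/dL | 8.5 | 8.0 |
| Neutrophils, 10⁹/L | 1.5 | 1.0 |
| Lymphocytes, 10⁹/L | 0.5 | 0.5 |
| WBC, 10⁹/L | 3.0 | 2.0 |

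Grade 3 low values of these four are thus screened out at entry. ALT and AST at 3.0 times the upper limit or more are also excluded, as is raised bilirubin. There is no numeric limit for glucose, creatinine, sodium, potassium, calcium, magnesium or platelets. None of these limits acts at Week 24. At Week 0 the issue therefore falls mainly on biochemistry. For liver tests it falls mainly on the switch.

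**3. What the shift tables cover**

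Table 12-1, headed "Definitions of CTCAE grades by biochemistry parameter", has creatinine, sodium, potassium, calcium and magnesium. Table 12-2 has the hematology parameters. Glucose has a markedly abnormal cut point in Table 10-1 but no grade row. ALT, AST and bilirubin have markedly abnormal thresholds but no grade rows. For these four, no shift table is specified that would separate old from new.

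**4. The 70-day split**

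The last adalimumab dose is at Week 23. Protocol 8.3 schedules biochemistry at Weeks 28, 32, 40, 48 and 56. On nominal dates these lie 5 × 7 = 35, 9 × 7 = 63, 17 × 7 = 119, 25 × 7 = 175 and 33 × 7 = 231 days later. A persistent abnormality can be counted at two visits in the first window and at three in the second.

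**5. Illustration for one parameter**

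Let n be the subjects, b the share markedly abnormal beforehand, r the share of those still abnormal afterwards, and e the new-onset rate in the rest. Only n comes from the documents: 300 pooled bimekizumab, and 150 adalimumab subjects if all switch. The values of b, r and e = 1% are assumptions.

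- Count under the SAP rule = n(1−b)e + nbr
- Count if Baseline must be below Grade 3 = n(1−b)e
- Carry-over = nbr

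| b | r | Carry-over, n = 300 | Carry-over, n = 150 | Share of SAP count |
|---|---|---|---|---|
| 0 | any | 0 | 0 | 0% |
| 0.5% | 25% | 0.38 | 0.19 | 11% |
| 1% | 50% | 1.50 | 0.75 | 34% |
| 2% | 75% | 4.50 | 2.25 | 60% |

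At the top of the range, with n = 300, the SAP count is 300 × 0.98 × 0.01 + 4.50 = 2.94 + 4.50 = 7.44, against 2.94 new cases.

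**The case against.** The strongest reply is that much of this can be seen elsewhere. Every Table 10-2 parameter, and every Table 10-1 parameter except glucose, has grade rows, so the shift tables separate pre-existing from new values. For switchers they already use the pre-switch value. Grade 3 and Grade 4 results are also listed, as are all laboratory data by subject. This stands for graded parameters. It does not stand for glucose and liver tests, and it does not correct the label on the count itself.

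Eligibility also does more than the numeric limits suggest. Exclusion 17a removes uncontrolled or unstable metabolic and renal disease, and 19f any other abnormality the investigator thinks disqualifying. Both lower b without guaranteeing zero. During treatment, the neutrophil and liver criteria in protocol 6.3 and 6.3.1 limit what can persist to Week 24. Section 6.3.1 nevertheless allows some subjects with raised transaminases to continue.

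Inclusive counting can be defended as conservative, and the rule is stated openly. Dropping everyone already at Grade 3 would hide a move from Grade 3 to Grade 4. That last point is sound and shapes the fix.

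A reader might infer that the randomised comparison is diluted. The documents do not support this. With b and r equal across randomised arms, the difference in rates is (1−b)(e₁−e₀), which at b = 2% keeps 98% of the new-onset difference. Only a ratio would be pulled towards one, and 10.3 plans neither a ratio nor a test.

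**Conclusion.** The point holds as one of definition. SAP 10.3 calls an abnormality treatment-emergent without asking whether it was already there, at Week 0 or at the switch. This is out of line with the SAP's own rules for adverse events and blood pressure. The consequence is a mislabelled count, most material for glucose, for liver tests and in the uncontrolled post-switch summary.

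The size is unknown. It is nil if nobody is markedly abnormal beforehand. Under the assumed ranges it is 0 to 4.5 of 300 pooled bimekizumab subjects and 0 to 2.25 of 150 switchers per parameter, up to 60% of the count when new onset is 1%.

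A reader might go further and take an assumed 1 to 3% of subjects with high Baseline glucose as 450 × 1% = 4.5 to 450 × 3% = 13.5 false cases. The documents give no such prevalence. That figure also requires every such subject to be abnormal again on treatment, since the Baseline value alone is never counted.

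These are descriptive safety tables, and no hypothesis in the testing sequence is affected. The change is worth making because it is cheap, not because a conclusion is at risk.

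**What to change.** In SAP 10.3, count a subject as treatment-emergent markedly abnormal only when the on-treatment value is markedly abnormal and of a higher grade than the applicable Baseline in the same direction. For glucose and liver tests, use a higher threshold category in place of grade. The applicable Baseline is Week 0, or the last value before the first bimekizumab dose for adalimumab-arm data after the switch. Apply the same rule to the 70-day summary and to the BKZ Set.

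Report subjects already markedly abnormal at Baseline in a separate row, so that a move from Grade 3 to Grade 4 stays visible. Add glucose and liver-test categories to the shift tables.

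If the rule is kept for consistency with other SAPs in the program, at least relabel the tables as post-Baseline markedly abnormal and still show the already-abnormal subjects separately.

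Both Baselines are already defined in SAP 3.2 and 10.3, and no new data are needed. The cost is SAP wording, slightly more programming and a small departure from the current table layout.

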10.4 Vital signs, physical findings, and other observations related to safety

10.4.1 Vital signs

The following vital signs variables should be summarized: systolic blood pressure (mmHg), diastolic blood pressure (mmHg), body temperature (°C) and heart rate (beats/min). The following summary will be provided:

- A summary of the absolute and change from Baseline value for each vital sign variable by treatment group and visit through initial and maintenance treatment period for the SS
- A summary of the number and percentage of subjects experiencing at least one markedly abnormal value for a vital sign variable as defined in Table 10–3, by treatment group, through Week 24 for the SS and through initial and maintenance treatment period for the BKZ set

Table 10–3: Definitions of Markedly Abnormal Blood Pressure Values

Parameter (unit)	Markedly Abnormal Low	Markedly Abnormal High
Systolic blood pressure (mmHg)	<90 and a decrease from Baseline of \geq 20	>180 and an increase from Baseline of \geq 20
Diastolic blood pressure (mmHg)	<50 and a decrease from Baseline of \geq 15	>105 and an increase from Baseline of \geq 15

A by-subject listing of all vital signs data should be provided. This listing should be presented by treatment group and will include: center, subject identifier, age, sex, race, weight, visit, vital sign variable and result (with abnormal values flagged as “L” or “H” accordingly).

10.4.2 Physical examination

Abnormal results of the physical examination together with details of abnormalities: abnormality clinically significant or not, will be listed by subject and visit.

10.4.3 Electrocardiograms

Electrocardiogram data will be analyzed by treatment group and visit for SS.

A summary of the number and percentage of subjects with normal and abnormal ECG results, as determined by the central reader, will be presented for all applicable visits.

The following ECG variables will be summarized (absolute values and change from baseline) by visit: QTcF, RR, PR, QRS and QT.

QTc outliers are defined as QTcF values following dosing that are greater than 450 ms or are increases from baseline greater than 30 ms. QTcF outliers will be highlighted in the data listings and summarized using the following categories:

- Values >450 ms, >480 ms, >500 ms
- Increase from baseline of >30 ms, increase from baseline of >60 ms, increase from Baseline of >90 ms
- Values >450 ms and increases of >30 ms. Values >500 ms and increases of >60 ms

The number and percentage of subjects who meet the ECG outlier criteria at any assessment post first dose will be summarized.

Two separate by-subject listings of all 12-lead ECG data will be provided based on interpretation from central reader and from site.

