5.2.3 Dose-blind Maintenance Treatment Period

After the 16-week Initial Treatment Period, subjects will enter the 40-week Maintenance Treatment Period. Treatment during the Maintenance Treatment Period will start at Week 16 and subjects will return to the clinic Q4W or Q8W through Week 56. The IMP will be administered in the clinic by sc injection at the time points specified in the schedule of study assessments (Table 5-1). Treatment during the Maintenance Treatment Period will be based on initial treatment per the following:

- Subjects in the bimekizumab 320mg Q4W treatment arm will continue to receive bimekizumab 320mg Q4W.
- Subjects in the bimekizumab 320mg Q4W/Q8W treatment arm will receive bimekizumab Q8W from Week 16 through Week 52.
- Subjects in the adalimumab treatment arm will receive bimekizumab 320mg Q4W from Week 24 to Week 52.

Subjects may receive placebo injections at certain visits in order to blind the IMP (see Section 7.2).

At the end of the Maintenance Treatment Period, all subjects enrolling in the open-label study will, after signing a new ICF, undergo the Week 56 study assessments and then receive their first dose of bimekizumab in the open-label study. All subjects not enrolling in the open-label study will have the Week 56 study assessments and will enter the SFU Period.

The assessments to be performed at each visit of the Maintenance Treatment Period are presented in Table 5-1.

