3.6 Treatment assignment and treatment groups

It is expected that subjects receive treatment as randomized and hence safety analyses will be based on the SS, as randomized. However, if after unblinding it is determined that subjects randomized to a treatment arm had never received such treatment, then for safety analyses, these subjects will be reallocated to the appropriate received treatment groups, unless otherwise specified.

Efficacy analyses should be performed according to randomized treatment and not actual treatment received.

Summaries based on SS or RS will be provided by “BKZ 320mg Q4W”, “BKZ 320mg Q4W/Q8W”, “BKZ Total” and “ADA” treatment groups. The ADA group will only be presented from Baseline to Week 24 in the by-visit summaries.

Summaries based on BKZ Week 24 set will be provided by “BKZ 320mg Q4W”, “BKZ 320mg Q4W/Q8W” and “ADA/BKZ 320mg Q4W” treatment groups for disposition, baseline assessments and efficacy. The ADA/BKZ 320mg Q4W group will be presented from Week 28 to Week 56 in the by-visit summaries for the PASI scores and the DLQI only.

For safety, summaries on the BKZ set will be provided by “BKZ 320mg Q4W”, “BKZ 320mg Q8W” and “BKZ Total”. BKZ Q4W will include data from subjects in the BKZ Q4W/Q8W arm (up to Week 16) and the ADA/BKZ Q4W arm (after Week 24).

Safety summaries on the BKZ Week 24 set will be provided for subjects switching from Adalimumab to Bimekizumab.

Summaries based on the Maintenance set will be provided by “BZK 320mg Q4W”, “BKZ 320mg Q4W/Q8W” and “BKZ Total”.

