10.4.4.2 Electronic Columbia Suicide Severity Rating Scale (eC-SSRS)

eC-SSRS questionnaire will be self-administered by the subject and assessed by trained study personnel. This scale will be used to assess suicidal ideation and behavior that may occur during the study. Results of the eC-SSRS will be summarized using the number of subject and percentage with (i) events in suicide behavior, (ii) suicidal ideation, (iii) suicidal behavior and ideation, and (iv) self-injurious behavior without suicidal intent.

Suicidal ideation is defined as an event in any of the following 5 categories:

- Wish to be dead
- Non-specific active suicidal thoughts
- Active suicidal ideation with any methods (not plan), without intent to act
- Active suicidal ideation with some intent to act, without specific plan
- Active suicidal ideation with specific plan and intent

Suicidal behavior is defined as an event in any of the following 4 categories:

- Actual attempt
- Interrupted attempt
- Aborted attempt
- Preparatory acts or behavior

Suicidal behavior or ideation is defined as an event in any of the above 9 categories.

Self-injurious behavior without suicidal intent is defined as an event in the category non-suicidal self-injurious injuries.

The incidence of subjects with suicidal ideation, suicidal behavior, suicidal ideation or behavior, and self-injurious behavior will be summarized by treatment group through week 24 and through initial and maintenance treatment period.

A by-subject listing of the eC-SSRS questionnaire data will be provided by treatment group.

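### Read literally, the cross-visit QTcF outlier count in SAP 10.4.3 places ECGs recorded on bimekizumab after the Week 24 switch under adalimumab

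*SAP*

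**What the plan says.** SAP 10.4.3 opens with the set and grouping: "Electrocardiogram data will be analyzed by treatment group and visit for SS". It then defines the event: "QTc outliers are defined as QTcF values following dosing that are greater than 450 ms or are increases from baseline greater than 30 ms". After listing the categories, it sets the counting rule: "The number and percentage of subjects who meet the ECG outlier criteria at any assessment post first dose will be summarized". It names no last assessment, no Week 24 cut and no second analysis set.

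SAP 3.6 fixes how SS groups are formed: "It is expected that subjects receive treatment as randomized and hence safety analyses will be based on the SS, as randomized". Reallocation applies only to subjects who never received their randomized treatment. The SS groups are the two bimekizumab arms, their total, and ADA. The only time limit on ADA is: "The ADA group will only be presented from Baseline to Week 24 in the by-visit summaries".

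Protocol 5.2.3 sets the switch: "Subjects in the adalimumab treatment arm will receive bimekizumab 320mg Q4W from Week 24 to Week 52".

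Neighbouring SAP sections do divide the data. Markedly abnormal laboratory values (10.3) and markedly abnormal vital signs (10.4.1) are each given for the SS through Week 24 and for the Bimekizumab Set through the initial and maintenance period. For the full-period laboratory shift tables, 10.3 adds: "For subjects randomized to ADA, only data after the switch to Bimekizumab will be considered".

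**The concern.** A count of subjects with an outlier at any assessment pools visits, so a limit written for by-visit summaries does not reach it. With as-randomized groups and no end of period, an adalimumab subject whose first outlier occurs at Week 36, 48 or 56 enters the ADA numerator although the subject was then taking bimekizumab. The AE rule in SAP 10.2 that moves events to the new treatment is written for adverse events only.

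There are two consequences. The ADA percentage is not an adalimumab percentage, and any difference in outlier risk between the drugs is diluted, which is the unhelpful direction for a safety comparison. The post-switch ECGs also enter no bimekizumab group, because 10.4.3 plans no Bimekizumab Set table.

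**Working it through.** The plan states no figure for ECG outliers, so there is none to reproduce.

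**ECGs under each drug.** Protocol Section 8 schedules post-dose ECGs at Weeks 12, 24, 36, 48 and 56. The Week 24 ECG is recorded before that visit's dose (8.3.4), so it belongs to adalimumab.

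- On adalimumab: Weeks 12 and 24, which is 2.
- On bimekizumab: Weeks 36, 48 and 56, which is 3.
- Share of a completer's post-dose ECGs taken on bimekizumab: 3/5 = 60%.

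Residual adalimumab does not blur this. The last adalimumab dose is at Week 23 and the first post-switch ECG is at Week 36, so the gap is 13 × 7 = 91 days. With the visit windows at their extremes (3 and 7 days) it is at least 81 days. The SAP uses 70 days as about five adalimumab half-lives (10.2.1).

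**Bimekizumab ECGs outside any bimekizumab group.** If all subjects complete, 150 × 3 = 450 post-switch ECGs sit under ADA. The two bimekizumab arms contribute 300 × 5 = 1,500. So 450 of 1,950 scheduled ECGs on bimekizumab (23%) are left out of every bimekizumab group.

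**Effect on the comparison.** Assume independent ECGs with a constant per-ECG outlier risk: a on adalimumab and b on bimekizumab. The documents give neither, so several pairs are shown.

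- Through Week 24: ADA = 1 − (1−a)²; BKZ = 1 − (1−b)²
- Five ECGs per arm, attributed to the drug taken: ADA = 1 − (1−a)⁵; BKZ = 1 − (1−b)⁵
- As written: ADA = 1 − (1−a)²(1−b)³; BKZ = 1 − (1−b)⁵

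The second row is hypothetical, because no one takes adalimumab after Week 24. It separates the effect of a longer window from that of attribution.

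| a, b | Through Week 24: ADA, BKZ (ratio) | Five per arm, by drug taken: ADA, BKZ (ratio) | As written: ADA, BKZ (ratio) |
|---|---|---|---|
| 3%, 6% | 5.9%, 11.6% (2.0) | 14.1%, 26.6% (1.9) | 21.9%, 26.6% (1.2) |
| 2%, 4% | 4.0%, 7.8% (2.0) | 9.6%, 18.5% (1.9) | 15.0%, 18.5% (1.2) |
| 2%, 1% | 4.0%, 2.0% (0.5) | 9.6%, 4.9% (0.5) | 6.8%, 4.9% (0.7) |
| 2%, 2% | 4.0%, 4.0% (1.0) | 9.6%, 9.6% (1.0) | 9.6%, 9.6% (1.0) |

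Lengthening the window alone takes the ratio only from 2.0 to 1.9. Attribution takes it from 1.9 to 1.2. On the difference scale (before rounding), the 3%, 6% row gives 5.7 points through Week 24, 12.5 points with correct attribution, and 4.8 points as written.

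**Share of ADA outliers that arise after the switch.** With equal risk p on both drugs, the share of ADA outlier subjects whose only outliers follow the switch is [(1−p)² − (1−p)⁵] / [1 − (1−p)⁵]. For p = 1% this is 2.91/4.90 = 59%, and for p = 10% it is 21.95/40.95 = 54%.

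**The case against.** The best defence is that 10.4.3 opens with analysis by treatment group and visit, which brings in the Week 24 limit of 3.6, and that a programmer could carry this limit through the whole section. That protects the by-visit ECG tables. It does not settle the closing sentence, which counts across visits. No actual miscount has been shown: the SAP could be programmed sensibly despite its wording.

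Four stronger readings are tempting, and the documents do not support them.

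- *That the trial has no clean QTcF comparison with adalimumab.* QTcF values, changes from baseline and central-reader results are planned by visit. There ADA stops at Week 24, so those summaries are uncontaminated.
- *That the whole fall in the ratio from 2.0 to 1.2 is misattribution.* Part of it is the longer window; the like-for-like contrast is 1.9 against 1.2. With equal risk on both drugs, both arms rise together and there is no bias between arms.
- *That the eC-SSRS table has the same fault.* SAP 10.4.4.2 says the incidence "will be summarized by treatment group through week 24 and through initial and maintenance treatment period". The Week 24 comparison is therefore planned, and only the names of the analysis sets are missing.
- *That post-switch increases must be measured from the last pre-switch ECG.* SAP 3.2 limits the bimekizumab baseline to PASI score, DLQI and laboratory shift tables, so this would be a new choice.

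It is also fair to say that ECG results are an other safety variable (Protocol 4.3.2), that QT is not a prespecified safety topic of interest (Protocol 12.1.1.4), and that the table is descriptive.

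**Conclusion.** The point holds for the cross-visit outlier count in SAP 10.4.3. Taken at its word, that count puts three of a completing adalimumab subject's five scheduled post-dose ECGs under the wrong drug, and no Bimekizumab Set outlier table corrects this. The 3-of-5 figure comes from the visit schedule and needs no assumption beyond completion. The attenuation of the ratio (1.9 to 1.2 when one drug has twice the other's risk in the two examples with higher bimekizumab risk) rests on assumed per-ECG risks and independence. Its direction is toward no difference whichever drug has the higher risk, and it vanishes if the risks are equal.

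The consequence is limited to a descriptive safety table. It deserves correction because the text departs from the sponsor's own practice for laboratory values and vital signs.

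**What to change.** In SAP 10.4.3, replace the open-ended count with two tables:

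1. SS, by treatment group, through Week 24, using assessments before the first dose on or after Week 24.
2. Bimekizumab Set, through the initial and maintenance period, counting only post-switch ECGs for subjects randomized to adalimumab. SAP 3.6 already assigns that arm's data after Week 24 to the bimekizumab Q4W safety group, and 10.3 and 10.4.1 already use this split of sets and periods for markedly abnormal values.

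State which baseline applies to post-switch increases. Under SAP 3.2 as it stands, it is the last value up to the first study dose, normally the Screening ECG because Protocol 8.2.1 lists none at the Baseline Visit. If the last pre-switch ECG is preferred, ECG must be added to the list in 3.2.

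The cost is a few sentences, one re-run table and one added table, with no change to data collection. The downside is that the comparative table then rests on two scheduled post-dose ECGs per subject instead of five.
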